
Trial objectives and purpose

The objectives of this study are to determine if the final product ENCOURAGE App can over a 6 month period:

- 1) Enhance physical activity levels; and,
- 2) Improve cardiovascular health risk;

Trial design

The public release of the ENCOURAGE App will involve two phases (Figure 1):

- 1) The recruitment of 300 individuals through the App. Any user will be able to download the ENCOURAGE App through the iTunes Store or Google Play. Note that when participants download the App, they are not automatically enrolled in the study. Participants will be prompted, after downloading the App, with a brief description of the study, as well as a pre-screening tool will be used to determine eligibility (see below for inclusion/exclusion criteria). Users will be asked via a textbox to determine if they wish to participate in a research project. Users will be asked to participate in a *time series quasi-experimental design* study to determine if the ENCOURAGE App can support participants to increase their physical activity levels over a 6 month period. The App uses a time management technique (i.e., Pomodoro technique) as a strategy to provide prompts for users to engage in an activity. The App can be customized by the users to set prompts at intervals that fits into their schedule. For example, these activities can range from a stretching activity (e.g., a neck stretch), a standing activity (e.g., stand and read), or a physical activity (e.g., fill up the printer with paper, do a squat). Additionally, the App will use Behavior Change Techniques as a way to support participants as they reduce their sedentary behavior and improve their physical activity levels.⁷ The App uses a series of Behavior Change Techniques shown to be effective in promoting a more physically active lifestyle.^{8,9} Users will also provide feedback regarding the App using an *experience sampling approach*, which uses a list of questions to guide user feedback (**Appendix 5**). Additionally, we will use *Flurry Analytics* (<http://www.flurry.com/>) to measure, track, and analyze the ENCOURAGE App performance, and aggregate-level user activity within the App. Specifically, we wish to determine the number of user sessions within the App, frequency of use, session length, user events, technical data and errors, and user geographic distribution. For a more detailed description of the experience sampling and Flurry Analytics approaches, see **Appendix 6**.

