The primary outcome for this time series quasi-experimental study is a change in moderate-vigorous physical activity within the subset of 60 participants. When doing a pre/post power analysis, an estimate of correlation between the pre and post measurements is required. We assumed a high correlation of 0.8 between measurements. Under this assumption, the sample size needed to detect a 20 minute/week increase for moderate-vigorous physical activity (Mean \pm SD; Pre: 72 \pm 64 min/week; Post: 92 \pm 86 min/week) is n=44 for with a two tailed α of 0.05 and power of 80%. Even so, we will recruit 60 participants to account for the possibility of drop out. If we assume a moderate correlation of 0.5 between Pre-Post, the sample size of 60 will still be large enough to detect a change in total physical activity (Pre: 1240 \pm 182 min/week; Post: 1402 \pm 455 min/week).

Study Data

For the experience sampling and Flurry Analytics approach to this study, data from participants at the aggregate level using the mobile App will be analyzed to categorize responses, generate frequency charts, and define themes

For the quasi-experimental design, a one-way repeated measures ANOVA or Mann-Whitney Test will be used to examine changes in breaks in sedentary time and other continuous outcome measures from baseline to 1 week, 1-month, 2-month, 3-month, 4-month, 5-month, and 6-month depending if the data are normally distributed. Categorical variables will be compared using a Chi-Square test. Relationships between variables will be assessed using Pearson or Spearman correlations, as well as multivariable linear or logistic regression.

Informed consent

The written consent form will be reviewed by the Health Research Ethics Board at the University of Manitoba prior to the initiation of the study. The consent form will describe the study procedures, risks and possible benefits, and will be reviewed by the participant prior to their enrollment in the study. Each participant will be asked to read the consent form and will be provided an opportunity to ask questions before they are enrolled. All participants will be required to provide written consent prior to initiation of study procedures. The consent form will be signed and dated by the participant and will be counter-signed by the researcher who conducted the informed consent process. The researcher will retain the original signed consent form and a copy of the form will be provided to the participant.

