(e.g., fast walking, baseball, tennis, easy bicycling, volleyball, badminton, easy swimming, alpine skiing, popular and folk dancing)

TIMES PER WEEK _____

c) MILD EXERCISE (MINIMAL EFFORT) (e.g., yoga, archery, fishing from river bank, bowling, horshoes, golf, snow-mobiling, easy walking)

TIMES PER WEEK _____

2. During a typical 7-Day period (a week), in your leisure time, how often do you engage in any regular activity long enough to work up a sweat (heart beats rapidly)?

OFTEN

SOMETIMES

NEVER/RARE

1.

2.

3.

CANHEART QUESTIONNAIRE – TOBACCO USE

1. Never used tobacco: 2. Ex-tobacco user: Quit date _____ 3.

Currently use:

If tobacco user, average number per day _____ and number of years _____

CANHEART QUESTIONNAIRE – FRUIT AND VEGETABLE CONSUMPTION

The next questions are about the foods you usually eat or drink. Think about all the foods you eat, both meals and snacks, at home and away from home.

1. How often do you usually drink fruit juices such as orange, grapefruit or tomato? (for example, once a day, three times a week, twice a month)

Times/day _____ OR Times/week _____

2. Not counting juice, how often do you usually eat fruit?

Times/day _____ OR Times/week _____

3. How often do you (usually) eat green salad?

Times/day _____ OR Times/week _____

4. How often do you usually eat potatoes, not including French fries, fried potatoes, or potato chips?

Times/day _____ OR Times/week _____

5. How often do you (usually) eat carrots?

Times/day _____ OR Times/week _____

6. Not counting carrots, potatoes, or salad, how many servings of other vegetables do you usually eat?

Times/day _____ OR Times/week _____

CANHEART QUESTIONNAIRE – HIGH BLOOD PRESSURE

1. We're interested in conditions diagnosed by a healthcare professional. Do you have high blood pressure? (please circle one)

Yes No

2. If yes, how old were you when you were first diagnosed?

Age in years _____

CANHEART QUESTIONNAIRE - DIABETES

1. We're interested in conditions diagnosed by a healthcare professional. Do you have diabetes? (please circle one)

Yes No

2. If yes, how old were you when you were first diagnosed?

Age in years _____

EXERCISE SELF-EFFICACY QUESTIONNAIRES**PHYSICAL ACTIVITY TASK SELF-EFFICACY QUESTIONNAIRE**

How certain are you that you can engage in moderate- to strenuous-intensity physical activity for the following durations? Please rate your degree of confidence for each duration using the scales.

10 minutes

0	1	2	3	4	5	6	7	8	9	10

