One area we wish to explore is whether you take breaks from your working tasks during work hours. During a typical working day there may be opportunities to take short physical activity breaks from your working tasks. This is any interruption to your sitting time at work. For example, taking time away from your desk/workstation to move around perhaps to get a drink, have a bathroom break or even continuing a work task while standing.

How many breaks from sitting (such as standing up, or stretching or taking a short walk) during one hour of sitting would you typically take at work?
(please circle the correct answer to the following questions)

a. During a typical work day how many breaks from sitting (such as standing up, or stretching or taking a short walk) during one hour of sitting would you take at work ?	6 or more	5	4	3	2	1	0
b. What is the total time you spend in short physical activity breaks during a typical day at work?	60 minutes or more	30- 59 min	20- 29 min	10- 19 min	5-9 min	Less than 5 min	N/A

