ENCOURAGE APP – statistical analysis plan:

For the primary outcome, a one-way repeated measures ANOVA or Mann-Whitney Test will be used to examine changes in the number of breaks in sedentary time from baseline to 1-month, depending if the data are normally distributed.

Other secondary, continuous outcome measures will be analyzed with a one-way repeated measures ANOVA or Mann-Whitney Test from baseline to 1 week, 1-month, 2-month, 3-month, 4-month, 5-month, and 6-month depending if the data are normally distributed. Categorical variables will be compared using a Chi-Square test. Relationships between variables will be assessed using Pearson or Spearman correlations, as well as multivariable linear or logistic regression.

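### Chi-Square is the only test named for categorical variables, yet several survey answers that fall to it by default are ordered; using the order is a cheap, minor improvement to secondary analyses

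*SAP*

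**What the plan says.** The SAP has two routes for change over visits. One is for continuous measures: "Other secondary, continuous outcome measures will be analyzed with a one-way repeated measures ANOVA or Mann-Whitney Test", chosen by normality. The other is a single sentence: "Categorical variables will be compared using a Chi-Square test". The protocol (Statistics, Study Data) repeats both. A rank test is therefore offered only for continuous outcomes. Regression, including logistic, is mentioned only for relationships between variables. Neither document names an ordinal, trend or paired categorical method, or lists the variables that count as categorical.

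The questionnaires in protocol Appendix 8 include these ordered answers:

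- **Workplace Sitting Breaks Questionnaire, item b:** "What is the total time you spend in short physical activity breaks during a typical day at work". There are six ordered bands, from under 5 minutes up to "60 minutes or more", plus an N/A option.
- **Godin questionnaire, question 2:** "in your leisure time, how often do you engage in any regular activity long enough to work up a sweat". There are three levels, from often down to never or rarely.
- **PHQ-9 item 10:** four grades of how difficult the problems made daily life.

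**The concern.** A Chi-Square statistic is unchanged if the bands are shuffled. On six bands it spreads its sensitivity over 5 degrees of freedom and asks whether the distributions differ in any way. The trial's question is whether people moved up. A significant result carries no direction and no effect size, and neither document asks for an estimate with an interval.

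Item b is the survey's only direct measure of time spent in short activity breaks, which is behaviour that the App prompts. Item a counts breaks per hour, and the occupational sitting questionnaire asks for percentages of the work day. Item b and Godin question 2 both bear on the first objective, enhancing physical activity. The stake is a real upward shift missed in a secondary analysis.

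This is separate from the fact that visits on the same person are not independent. A paired unordered test such as Stuart-Maxwell would cure that and still discard the order.

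**Working it through.** The plan states no power for any categorical outcome, so it has no figure of its own to reproduce here. The check isolates the loss of order by respecting the pairing in both tests.

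**Inputs from the protocol (Sample Size; Trial design)**
- Two-sided alpha 0.05; pre-post correlation r = 0.8, with 0.5 as the alternative.
- Survey n = 300; accelerometer sub-sample n = 60.
- Activity outcome 72 (SD 64) to 92 (SD 86) min/week. This gives two shifts in SD units: 20/64 = 0.3125, and 20/sqrt((64² + 86²)/2) = 20/75.8 = 0.264.

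**Assumptions (no figure in the documents)**
- The activity shifts carry over to the ordered items. Shifts of 0.15 and 0.20 SD are added as smaller cases.
- Baseline level shares are 15/20/20/20/15/10% for six bands and 35/45/20% for three levels.
- A latent bivariate normal with correlation r, equal SDs and mean shift d is cut at the baseline quantiles.

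**Step 1, degrees of freedom alone.** If the ordered test (1 df) has 80% power, its noncentrality is 7.85. At the same noncentrality a 5 df test has 55.5% power (loss 24.5 points) and a 2 df test 70.9% (loss 9.1). At 95% ordered power the figures are 80.6% (loss 14.4) and 90.8% (loss 4.2).

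**Step 2, simulation.** Stuart-Maxwell against Wilcoxon signed-rank with Pratt zeros, 3,000 replicates per setting; the standard error of each power is at most sqrt(0.25/3000) = 0.9 points. Cells give unordered % / ordered % (loss in points, taken before rounding).

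| Levels, n, r | d=0.15 | d=0.20 | d=0.264 | d=0.3125 |
|---|---|---|---|---|
| 6, 60, 0.5 | 9/20 (10) | 12/28 (16) | 22/45 (22) | 31/58 (27) |
| 6, 60, 0.8 | 15/35 (20) | 26/55 (29) | 48/78 (30) | 65/90 (25) |
| 6, 300, 0.5 | 41/67 (26) | 69/89 (20) | 93/99 (6) | 98/100 (1) |
| 6, 300, 0.8 | 80/95 (15) | 97/100 (2) | 100/100 (0) | 100/100 (0) |
| 3, 60, 0.5 | 11/16 (5) | 19/25 (6) | 29/37 (9) | 39/51 (12) |
| 3, 60, 0.8 | 18/25 (7) | 28/38 (9) | 48/61 (14) | 62/76 (14) |
| 3, 300, 0.5 | 46/57 (11) | 72/80 (8) | 94/97 (3) | 98/99 (1) |
| 3, 300, 0.8 | 74/82 (8) | 94/97 (3) | 100/100 (0) | 100/100 (0) |

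With d = 0, rejection was 3.4 to 5.3% for Stuart-Maxwell and 4.3 to 5.7% for signed-rank. The widest gap was 3.4% against 5.5% (six bands, n=60, r=0.8), so about 2 points of the loss in that row are test size and not order. Repeat runs with fewer replicates move single losses by up to about 3 points. The ranges quoted in the conclusion span them.

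**Step 3, other shares.** With six equal bands and the protocol's change divided by its SD of change at r = 0.8 (20/51.8 = 0.386), n=60 gives 39% against 72% (loss 33) and n=300 gives a loss of about 0.

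**Not counted here.** The ordinary Chi-Square on visit by level, which also ignores pairing, does worse still: about 14% at n=60 (six bands, d=0.3125, r=0.5) and 36% at n=300 (d=0.20, r=0.5).

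**The case against.** Four points can fairly be made for the plan.

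1. **The items are never assigned to Chi-Square.** Item a has the same circled-answer layout as item b, and the SAP sends a count of breaks to ANOVA or a rank test, so item b might be scored the same way. This stands: a reader might infer that the plan commits item b to Chi-Square, or counts N/A as a seventh level, and the documents say neither. What remains is an unassigned scale type with Chi-Square as the literal default. Scoring item b as continuous would also need a rule, because its bands are unequal and open-ended and N/A has no score.
2. **The survey has 300 participants.** The 60 are the accelerometer sub-sample. At 300, with the two shifts that derive from the documents, the loss is small. This also stands and limits the claim. The n=60 rows apply to an analysis of the sub-sample, or to a survey reduced to a fifth of its size (60/300). The documents give no attrition rate for the survey.
3. **None of these items is a named outcome.** The protocol's Sample Size section makes moderate-vigorous activity primary, and the SAP makes the number of breaks primary. Godin's main result is the weighted weekly score. Direction would be visible in tabulated proportions. All true, which is why this is minor.
4. **The ordinal method has assumptions too,** and a pure latent shift favours it. True, but a shift is what the objective asks about.

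**Conclusion.** The point holds as a minor improvement. The plan names one test for categorical variables; that test discards order, and at least three survey items are ordered.

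The size is conditional. Six bands lose roughly 10 to 32 points at n=60. At n=300 they lose about 0 to 7 points at shifts of 0.26 to 0.31 SD, and about 2 to 26 at 0.15 to 0.20 SD. Three-level items lose about 3 to 14 points at n=60 and 0 to 11 at n=300. All of this rests on assumed level shares, on shifts either borrowed from another outcome or simply assumed, and on correlations that the protocol gives for activity minutes and not for these items.

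A reader might infer a large loss of power for ordered answers in general. The documents do not support that: at the planned survey size, with the shifts that can be derived from them, the loss is close to nothing in most settings. Nor does the point touch either version of the primary outcome.

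**What to change.** In the SAP, and in the protocol's Study Data section:

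- Limit the unordered test to nominal and yes/no items.
- List the ordered items (sitting-breaks item b, Godin question 2, PHQ-9 item 10) and give them one pre-specified method that uses both order and pairing. The preferred choice is a cumulative-logit model with a person random effect across the 8 survey occasions, reporting the odds ratio for a higher level with its 95% CI. The simpler alternative is a Wilcoxon signed-rank test at one named visit. Testing every follow-up against baseline would mean 7 tests per item, or 21 for three items, with no multiplicity rule.
- Treat N/A on item b as outside the ordered scale and report its count at each visit. The item has no zero band, so also state what N/A is taken to mean.

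**Cost:** wording only, with no new data, participants or visits. Both ordinal methods are less sensitive to a change in spread without a shift, which is not the trial's question. The model assumes proportional odds. The signed-rank version treats a one-band move as equal across bands of unequal width.
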